7.2.1. Secondary Efficacy Endpoints based on SUA

For the following secondary endpoints, the comparison between SEL-212 and KRYSTEXXA® will be done similar to the primary efficacy endpoint using a CMH-test considering the randomization stratum of tophus presence (yes/no) with one-sided type 1 error rate level of $\alpha=5\%$. In addition, 90% confidence intervals for treatment differences between SEL-212 and KRYSTEXXA® treatment groups will be computed. The efficacy analyses will be carried out based on the ITT and PP Sets. mITT analyses will be performed as supportive.

- percentage of patients who achieve and maintain reduction of SUA < 6 mg/dL for at least 80% of the time during Treatment Period 3
- percentage of patients who achieve and maintain reduction of SUA < 6 mg/dL for at least 80% of the time during Treatment Period 6
- percentage of patients who achieve and maintain reduction of SUA < 6 mg/dL for 100% of the time during Treatment Period 6
- percent of patients whose pre-dose SUA values > 6 mg/dL during Treatment Periods 2-6

A summary table of the number and percentage of patients who achieve and maintain reduction of SUA < 6 mg/dL for at least 80% of the time during Treatment Period 6 will be provided by treatment group.

A summary table of the number and percentage of patients who achieve and maintain reduction of SUA < 6 mg/dL for at least 80% of the time during Treatment Period 3 will be provided by treatment group.

A summary table of the number and percentage of patients who achieve and maintain reduction of SUA < 6 mg/dL for 100% of the time during Treatment Period 6 will be provided by treatment group.

A summary table of the number and percentage of patients who achieve and maintain reduction of SUA < 6 mg/dL for 100% of the time during Treatment Period 3 will be provided by treatment group.

A summary table of the number and percentage of patients with pre-dose SUA values > 6 mg/dL during Treatment Periods 2-6 will be provided by treatment group.

This document is confidential.

7.2.2. Change from baseline in HAQ-DI Total Score

The HAQ-DI, which includes the patient global assessment and pain scale, is an instrument that assesses fine movements of the upper extremity, locomotor activities of the lower extremity, and activities that involve both the upper and lower extremities. Standard scoring takes into account the use of aids and devices or assistance from another person. There are 20 items in 8 categories that represent a comprehensive set of functional activities: dressing, rising, eating, walking, hygiene, reach, grip, and usual activities. The stem of each item assesses a patient's functional ability using their usual equipment during the past week. Each category contains at least 2 specific sub-category questions. For example, under the category "walking," patients are asked about their ability to walk outdoors on flat ground and to climb up 5 steps.

Eight (8) categories will be assessed by the HAQ-DI: 1) dressing and grooming, 2) arising, 3) eating, 4) walking, 5) hygiene, 6) reaching, 7) gripping, and 8) common daily activities. There are 2 or 3 questions for each section. Scoring within each section is on a 4-point Likert scale from 0 (without any difficulty) to 3 (unable to do). The score given to each section is the worst (highest) score within the section (ie, if one question is scored 1 and another 2, then the score for the section is 2). In addition, if an aid or device is used or if help is required from another individual, then the minimum score for that section is 2. If the section score is already 2 or more then no modification is made. The sum of the 8 scores of the 8 sections will be divided by 8 to obtain the HAQ-DI total score. In the event that one section is not completed by a subject then the summed score would be divided by 7. The HAQ-DI total score will be calculated if 6 or more sections are available.

Comparison with regards to change from baseline will be performed using an ANCOVA with the respective change from baseline value as dependent variable, treatment group and the randomization stratum as independent fixed factors and the baseline value as independent covariate.

Summary tables of total scores will be provided for each scheduled assessment time by treatment group. Additionally, summaries of the changes from baseline will be provided.

7.2.3. Provider Global Assessment of Disease Activity (PrGA)

The PrGA will be administered to assess the severity of the patient's disease on a scale from 0 (patient feels "very well") to 100 (patient feels "very poor"). Lower scores indicate less severe disease.

Comparison with regards to change from baseline in PrGA will be performed using an ANCOVA with the respective change from baseline value as dependent variable, treatment group and the randomization stratum as independent fixed factors and the baseline value as independent covariate.

Summary tables of PrGA will be provided for each scheduled assessment time by treatment group. Additionally, summaries of the changes from baseline will be provided.

7.2.4. Short Form Health Survey 36 (SF-36)

The SF-36 is a 36-item scale constructed to survey health status and quality of life ([Ware 1992](#)). The SF-36 assesses 8 health concepts: limitations in physical activities because of health problems; limitations in social activities because of physical or emotional problems; limitations in usual role activities because of physical health problems; bodily pain; general mental health (psychological distress and well-being); limitations in usual role activities because of emotional problems; vitality (energy and fatigue); and general health perceptions. The standard form of the instruments asks for patients to reply to questions according to how they have felt over the previous week.

This document is confidential.

Statistical Analysis Plan

Sponsor: Selecta Biosciences

Protocol No.: SEL-212/202

The SF-36 consists of 8 scaled domain scores with range 0-100 with higher score indicating better health and 2 component scores (physical component and mental component). The 8 domains are:

- Vitality
- Physical functioning
- Bodily Pain
- General Health Perceptions
- Physical Role Functioning
- Emotional Role Functioning
- Social Role Functioning
- Mental Health

All domain scores and component scores will be derived and collected on eCRF.

For each domain and component scores, comparison with regards to change from baseline will be performed using an ANCOVA with the respective change from baseline value as dependent variable, treatment group and the randomization stratum as independent fixed factors and the baseline value as independent covariate.

Summary tables of each domain and component score will be provided for each scheduled assessment time by treatment group. Additionally, summaries of the changes from baseline will be provided.

7.2.5. Gout Flares Incidence and Frequency

The number and percentage of patients reporting gout flares per 3-months period and overall, i.e. Treatment Periods 1-3, Treatment Periods 4-6 and Periods 1-6, will be summarized by treatment group and will be tested using a CMH-test considering the randomization stratum. The same analysis will also be performed by patient's maximum severity of gout flare experienced within each 3-months period.

The frequency of gout flares will be summarized per 3-months period and overall and by severity for each treatment group and will be compared using ANOVA model with presence of tophus and treatment group as fixed factors. In addition for periods 4-6 and 1-6, poisson regression model will be used with number of gout flares as independent variable, treatment and presence of tophus as fixed factor, and length of follow-up for each corresponding treatment period as covariate.

7.2.6. Change from Baseline to Treatment Period 6 in Number of Tender and Swollen Joints

Comparison with regards to change in number of tender joints from baseline to end of treatment period 3 (day 0 period 4) and period 6 will be performed using an ANCOVA with the change from baseline value as dependent variable, treatment group and randomization stratum as independent fixed factors and the baseline number of tender joints as independent covariate. In case of non-normality the non-parametric Wilcoxon test will be used for the comparison between the treatment groups. Summary tables of the number of tender joints for each assessment time point and for the change from baseline will be provided by treatment group.

Comparison with regards to change of swollen joints from baseline to end of treatment period 3 (day 0 period 4) and 6 will be performed using an ANCOVA with the change from baseline value as dependent variable, treatment group and randomization stratum as independent fixed factors and the baseline number of swollen joints as independent covariate. In case of non-normality, the non-parametric Wilcoxon test will be used for the comparison between the treatment groups. Summary tables of the number of

This document is confidential.

swollen joints for each assessment time point and for the change from baseline will be provided by treatment group.

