Summary table of the number and percentage of subjects who achieve and maintain reduction of SUA < 6 mg/dL for at least 80% of the time during Treatment Period 6 will be provided by treatment group. The comparison between the treatment groups will be performed similar to the primary efficacy endpoint using a CMH-test considering the randomization stratum.

Summary table of the number and percentage of subjects who achieve and maintain reduction of SUA < 6 mg/dL for 100% of the time during Treatment Period 6 will be provided by treatment group. The comparison between the treatment groups will be performed similar to the primary efficacy endpoint using a CMH-test considering the randomization stratum.

Summary table of the number and percentage of subjects with pre-dose SUA values > 6 mg/dL during Treatment Periods 2-6 will be provided by treatment group. The comparison between the treatment groups will be performed similar to the primary efficacy endpoint using a CMH-test considering the randomization stratum.

For the health questionnaires, comparison with regards to change from baseline in health questionnaires will be performed using an ANCOVA with the respective change from baseline value as dependent variable, treatment group and the randomization stratum as independent fixed factors and the baseline value as independent covariate.

For each health questionnaire, summary tables of total scores or domain scores and subscale scores will be provided for each scheduled assessment time by treatment group. Additionally, summaries of the changes from baseline will be provided.

The number and percentage of subjects reporting gout flares per 3-months period and overall, i.e. Treatment Periods 1-3 and Treatment Periods 4-6 and Period 1-6, will be summarized by treatment group and will be tested using a CMH-test considering the randomization stratum.

The frequency of gout flares will be summarized per 3-months period and overall and by severity for each treatment and will be compared using ANOVA model with presences of tophus and treatment as fixed factors. In addition for periods 4-6 and 1-6, poisson regression model will be used with number of gout flares as independent variable, treatment and presence of tophus as fixed factor, and length of follow-up for each corresponding treatment period as covariate.

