5.3. Intent-to-Treat Set

The Intent-to-Treat (ITT) Set will be used as the primary population for the analysis of efficacy. The ITT Set will include all randomized patients. Patients will be analyzed according to randomized treatment. ITT set is same as randomized set by its definition and will be referred as so in this SAP.

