5.9. Missing Data

Missing data will not be imputed unless specified otherwise. Missing eCRF data due to Covid-19 will be listed.

This document is confidential.

6. Demographic, Other Baseline Characteristics and Medication

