7.4. Deviation from Analyses Planned in Protocol

7.4.1. Additional analyses

The following analyses are added even though they are not included in the protocol:

- Interim analysis.
- Subgroup analyses on the secondary endpoint by patient's primary efficacy endpoint (responder vs. non-responder).

The following analyses have been added as a result of the impact of Covid-19 on the study which may result in a larger anticipated number of subjects not completing the study and therefore not undergoing the assessments required for the primary efficacy endpoint or the study being stopped prematurely by sponsor decision. This is in line with FDA Guidance on Conduct of Clinical Trials of Medical Products during COVID-19 Pandemic Guidance for Industry, Investigators, and Institutional Review Boards.

- Additional analyses suggested to primary endpoint as sensitivity analyses to determine if the impact that these have on the conclusions of the study and to describe the impact of Covid-19 on the study performance.
- A sensitivity analysis which limited the analysis to results processed in the central laboratory to determine if this resulted in different conclusions to those found from the full analysis to determine consistency in laboratory testing between central and local laboratories.
- Kaplan-Meier analysis of withdrawal from study by treatment arm and presence of tophus to determine if subjects withdraw from the study in different proportions and at different rates within the treatment groups and depending on the presence of tophus.
- Kaplan-Meier analysis of withdrawal from study due to an adverse event by treatment arm and presence of tophus to determine if subjects experience adverse events in different proportions and at different rates within the treatment groups and depending on the presence of tophus.
- Poisson regression with number of gout flares experienced during treatment periods 1-6 as the dependent variable, treatment and the presence of tophus as independent variables and length of follow up as a covariate. The ITT population would be used to conduct this analysis. Similar analysis is done for periods 4-6.

This document is confidential.

8. Safety

The population used for safety analyses will be the Safety Set (SS). Safety will be assessed on the basis of adverse event (AE), clinical laboratory data, ECG parameters, physical examinations, and vital signs.

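### The gout flare incidence test ignores time at risk, so unequal study withdrawal can pass for a difference in flares, and the TP4-6 denominator for patients who left earlier is not settled

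*SAP*

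**What the plan says.** Flare incidence per three-month window is a secondary endpoint, listed separately from flare frequency (Protocol 6.2.2, SAP 4.2). In SAP 7.2.5 the share of patients with a flare in TP1-3, TP4-6 and TP1-6 "will be summarized by treatment group and will be tested using a CMH-test considering the randomization stratum". Protocol 13.4.2 agrees: it "will be tested using a CMH-test considering the randomization stratum". Neither place has a follow-up term or a rule for patients who leave. Protocol 13.4.2 makes secondary tests one-sided at 5%, on the ITT and PP sets.

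For frequency, SAP 7.2.5 says that counts "will be compared using ANOVA model with presence of tophus and treatment group as fixed factors". For TP4-6 and TP1-6 it adds a Poisson model with "length of follow-up for each corresponding treatment period as covariate". SAP 7.4.1 says of that model: "The ITT population would be used to conduct this analysis".

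On loss, SAP 7.4.1 says that Covid-19 "may result in a larger anticipated number of subjects not completing the study" and adds Kaplan-Meier curves of study withdrawal by arm and tophus.

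On who is counted, SAP 5.3 says "The ITT Set will include all randomized patients" and SAP 5.9 says "Missing data will not be imputed unless specified otherwise". The table conventions in SAP 11.2.5.2 take as the default percentage denominator only those patients in the set who have an observation.

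On collection, flares are captured with TEAEs (Protocol 11.2.1), and AE reporting stops 30 days after the last infusion (Protocol 12.2.3.1). Yet flares are assessed at every visit (Protocol 7.1.2), and patients taken off drug continue visits to the end of TP6 (Protocol 7.4.1.1 and 7.4.1.2).

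**The concern.** A share of patients with at least one event is comparable between arms only if the arms are observed for similar lengths of time. A patient who leaves in week 2 of a 12-week window without a flare enters the CMH table exactly like a patient watched for all 12 weeks without one. If one arm has more such patients, its incidence falls for a reason unrelated to flares. A lower incidence in one arm then cannot be told apart from shorter observation, and the one-sided 5% error rate is not held. The SAP anticipates loss, and plans to look at whether it differs by arm, but carries follow-up time only into the Poisson model for counts.

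**Working it through.** **The plan's own figure.** The documents give no figure for the flare endpoint. The only sample-size figure is for the primary endpoint: 65% vs 44%, one-sided 5%, 80% power. It reproduces at 69 per group (pooled variance, no continuity correction; power 80.3%). It matters here only because it leads to 75 randomized per arm.

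**Inputs.**
- From the documents: 75 per arm (Protocol 13.1, SAP 3.5), one-sided 5%, windows of 84 days (TP1-3, TP4-6) and 168 days (TP1-6).
- Assumed: the same true flare rate in both arms, mean m = 0.8 flares per 84 days (1.6 per 168 days); 20% leaving in one arm and 5% in the other; leaving unrelated to flares. The documents give no leaving rate by arm. The tophus stratum is left out because its distribution is not given.

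**Formulas.**
- Full follow-up: f = 1 − exp(−m).
- Leaving evenly over the window: a leaver has a recorded flare with probability 1 − f/m, so observed incidence = (1 − d)·f + d·(1 − f/m), with d the share leaving.
- All leavers gone before TP4 and kept as flare-free: observed incidence = (1 − d)·f.
- All leavers gone before TP4 and dropped: f in both arms, on 75 × 0.80 = 60 and 75 × 0.95 ≈ 71 patients.
- Rejection: exact binomial enumeration, pooled one-sided z-test at 1.645, in favour of the higher-loss arm.

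**Numbers.** For 84 days, f = 1 − exp(−0.8) = 0.551 and a leaver's probability is 1 − 0.551/0.8 = 0.312. For 168 days, f = 1 − exp(−1.6) = 0.798 and a leaver's probability is 1 − 0.798/1.6 = 0.501.

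| Case | Higher-loss arm (20%) | Lower-loss arm (5%) | Test favours higher-loss arm |
|---|---|---|---|
| Three-month window, leaving spread over it | 0.80×0.551 + 0.20×0.312 = 50.3% | 0.95×0.551 + 0.05×0.312 = 53.9% | 10.5% |
| TP1-6, leaving spread over 168 days | 0.80×0.798 + 0.20×0.501 = 73.9% | 0.95×0.798 + 0.05×0.501 = 78.3% | 16.0% |
| TP4-6, all gone before TP4, kept as flare-free | 0.80×0.551 = 44.1% | 0.95×0.551 = 52.3% | 24.8% |
| TP4-6, all gone before TP4, dropped | 55.1% | 55.1% | 5.0% |

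In the first two rows the choice of denominator makes no difference, because everyone has been observed for part of the window. In the last two rows it is the whole story.

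**Sensitivity.** At 15% vs 5% leaving, the first row becomes 8.2% and the third 15.3%. For means of 0.4 to 1.6 per 84 days at 20% vs 5%, the first row runs from 9% to 16%. The only flare rate in the documents is 7 per year (Protocol 5.4), which is 7 × 84/365.25 = 1.6 per 84 days; at that rate the third row is about 49%. If the loss is reversed, so that the comparator arm loses 20% and SEL-212 loses 5%, the third row's chance of favouring SEL-212 falls to 0.3%.

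**Does time to first flare repair it?** A simulation (3000 runs per scenario, equal true rates of 2 to 7 per year, 20%, 30% or 40% lost vs 10%) compared the simple share with an unstratified log-rank test censoring leavers. The log-rank test rejected in 4.3% to 5.9% of trials throughout. At 7 per year and 30% vs 10%, the simple share rejects in 20.7% (three-month window, loss spread), 29.1% (TP1-6, loss spread) and 65.6% (TP4-6, gone before and kept); the log-rank test rejects in 5.2%, 4.3% and 5.3%.

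**End of flare collection.** A patient withdrawn from drug after the first infusion reaches the end of AE reporting at about Day 30, but has visits with flare assessment to Day 168. Under the first rule TP1-3 holds 30 of 84 days of flare observation; under the second, all 84. The stopping rules differ by arm, so this too could shorten observation unequally, even among patients who stay in the study.

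**The case against.** Four objections have weight.

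First, a reader might infer that every patient who leaves is counted flare-free, including one gone before TP4. The documents do not say so. SAP 5.9 rules out imputation by default, and SAP 11.2.5.2 could remove such a patient from the TP4-6 percentage, in which case the calculation shows no inflation. A leaver who flared earlier in the window is counted correctly. This stands, and it confines the 25% figure to one reading of an unsettled rule. It does not reach loss within a window.

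Second, the SAP already has a follow-up-adjusted flare analysis. For counts in TP4-6 and TP1-6 that is true, and it softens the consequence. It does not test incidence, and TP1-3 has no follow-up-adjusted analysis at all.

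Third, unequal loss is hypothetical. SAP 7.4.1 expects more non-completers overall, not more in one arm. Patients off drug stay in the study, and Protocol 8.2.1.3.1 discourages investigators from terminating dosed patients. This limits loss without excluding it. A reader might also infer that the bias favours SEL-212; nothing in the documents says which arm will lose more.

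Fourth, incidence is one of many secondary endpoints, and SAP 7.2 gives them no hierarchy. That bears on priority, not on whether the test is sound.

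**Conclusion.** The concern holds in a conditional form. The incidence test uses no time at risk, so if study withdrawal differs by arm and is unrelated to flare risk, it favours the arm that loses more. At 20% vs 5% leaving and 0.8 flares per 84 days, the nominal 5% becomes about 10% in a three-month window and about 16% over TP1-6, whichever denominator is used. For TP4-6 with leaving before TP4 it is about 25% or 5%, depending on a denominator that the plan leaves open. With equal leaving in the two arms the error rate is not inflated. The sizes rest on assumed leaving rates and flare means; the existence of the effect for loss within a window does not. This is worth correcting before the analysis is run, but it does not touch the primary endpoint.

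**What to change.** In SAP 7.2.5, test incidence in each window as time to first flare:
- Patients are at risk from TP1 Day 0 for TP1-3 and TP1-6, and from TP4 Day 0, if still in the study, for TP4-6.
- Censor at the end of flare observation or the end of the window, whichever comes first.
- Use a log-rank test stratified by tophus, and report the Kaplan-Meier incidence at the end of each window with a 90% confidence interval by arm.
- Keep the raw percentages as description, and state their denominator in each window, including how patients gone before TP4 are counted.

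Reconcile AE reporting that ends 30 days after the last infusion (Protocol 12.2.3.1) with flare assessment at visits through TP6 (Protocol 7.1.2, 7.4.1.1 and 7.4.1.2), because this sets the censoring time.

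The cost is SAP wording and one more run of the stratified log-rank and Kaplan-Meier methods already planned in SAP 6.1. The downside is that censoring assumes leaving is unrelated to an imminent flare within arm and stratum. The raw share assumes more: that a leaver would have had no later flare in the window.

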7.2. Secondary Efficacy Endpoint Analyses

There is no hierarchical ordering of the secondary endpoints. All secondary endpoint will be included for analyses as described.

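### The Poisson model for gout flare frequency makes no allowance for overdispersion, and the raw-count ANOVA, the only frequency test for Treatment Periods 1-3, takes no account of observed time

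*SAP*

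**What the plan says.** SAP 7.2.5 says that flare counts per three-month period and overall "will be compared using ANOVA model with presence of tophus and treatment group as fixed factors". It adds a Poisson regression for TP4-6 and TP1-6, with treatment and tophus as factors "and length of follow-up for each corresponding treatment period as covariate". TP1-3 therefore has only the ANOVA. Incidence (any flare) is tested by CMH stratified by tophus. Protocol 13.4.2 has the same scheme: "In addition for periods 4-6 and 1-6, poisson regression model will be used with number of gout flares as independent variable".

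SAP 7.4.1 lists the model as "Poisson regression with number of gout flares experienced during treatment periods 1-6 as the dependent variable", among analyses added because Covid-19 "may result in a larger anticipated number of subjects not completing the study". It adds: "The ITT population would be used to conduct this analysis". None of the three places names a scale parameter, robust variance, a negative binomial alternative or an offset.

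On missing data, SAP 5.9 says: "Missing data will not be imputed unless specified otherwise". On status, SAP 7.2 says: "There is no hierarchical ordering of the secondary endpoints". Protocol 13.4.2 sets all secondary tests at one-sided 5%.

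**The concern.** Flares are a secondary objective, and patients with refractory gout are likely to differ in their underlying flare rates. A Poisson model without dispersion handling treats all patients with the same covariates as having one rate. If they do not, its standard errors are too small and its p-values too favourable, in whichever direction the data fall.

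The ANOVA has the opposite weakness. It estimates its own variance, so overdispersion does little harm, but a patient seen for 20 days and one seen for 84 days enter on the same footing. The SAP expects more non-completers and adds the Poisson model in response, yet that model does not reach TP1-3. So the frequency test that copes with unequal time mishandles dispersion, and the one that copes with dispersion ignores time.

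A related gap is when flare counting ends after drug is stopped. Protocol 11.2.1 collects flares as treatment-emergent adverse events, which Protocol 12.2.1.1 and 12.2.3.1 and SAP 8.3 end 30 days after the last dose. Protocol 7.1.2, 7.4.1.1, 7.4.1.2, 8.2.1.3.1 and Appendices A and C keep patients under visits, with flare assessment, to the end of TP6. Follow-up length is not defined.

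**Working it through.** **Plan's own figure.** The documents give no power, flare rate or dispersion for flares. The only sample-size figure is for the primary endpoint (Protocol 13.1: 65% vs 44%, one-sided 5%, 80% power). A pooled chi-square calculation without continuity correction reproduces its 69 per arm. I use the 75 per arm to be randomised.

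**Assumed inputs.** Protocol 5.4 gives a background of 7 flares a year: 7 × 84/365.25 = 1.61 per 84 days. This is probably high here, given prophylaxis (Protocol 10.5.1) and the lower flare rates reported on SEL-212 (7.6.3.2, 7.7), so I also use 0.8 and 0.4. Between-patient variation is gamma with shape 1, 2 or 4 (a smaller shape means more variation). True rates are equal in both arms throughout.

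**Step 1: Poisson, full follow-up.** With mean m and gamma shape s, the count variance is m(1 + m/s), while the model assumes m. The one-sided error is therefore

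1 − Φ(1.645 / √(1 + m/s)), with 2m in place of m for TP1-6.

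Example, m = 1.6 and s = 2. TP4-6: 1.645/√1.8 = 1.226, giving 11.0%. TP1-6: 1.645/√2.6 = 1.020, giving 15.4%.

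| Mean per 84 days | TP4-6, shape 1 / 2 / 4 | TP1-6, shape 1 / 2 / 4 |
|---|---|---|
| 1.6 | 15.4 / 11.0 / 8.2% | 21.1 / 15.4 / 11.0% |
| 0.8 | 11.0 / 8.2 / 6.7% | 15.4 / 11.0 / 8.2% |
| 0.4 | 8.2 / 6.7 / 5.8% | 11.0 / 8.2 / 6.7% |

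With no extra variation the error is 5%. Simulated trials agree within 2 points. In them the ANOVA stays at 4-6% with full follow-up.

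**Step 2: unequal dropout, shape 2.** Assume 10% of one arm and 30% of the other leave the study, at a time uniform over 0-168 days. A leaver contributes on average 21 days to TP4-6 (half contribute none, half average 42) and 63 days to TP1-3.

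- TP4-6, no-time patients counted as zero: mean days are 0.9 × 84 + 0.1 × 21 = 77.7 and 0.7 × 84 + 0.3 × 21 = 65.1. At mean 1.6 the false difference is 1.6 × 12.6/84 = 0.24 flares. The standard error is about √(2 × 2.88/75) = 0.277, where 2.88 = 1.6 × 1.8. The ratio is 0.87, so the error is about 1 − Φ(1.645 − 0.87) = 22%.
- TP4-6, no-time patients left out: mean days are 77.7/0.95 = 81.8 and 65.1/0.85 = 76.6. The false difference is 1.6 × 5.2/84 = 0.10, with standard error about 0.29. The error is about 10%.
- TP1-3: mean days are 81.9 and 77.7. The false difference is 0.08, and the error is about 9%.

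Simulation (70% tophus, from Protocol 5.4; means 0.4 to 1.6) gives:

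| Case | ANOVA | CMH incidence |
|---|---|---|
| TP4-6, 10% vs 30%, left out | about 7-11% | about 7-11% |
| TP4-6, 10% vs 30%, counted as zero | 14-24% | 15-32% |
| TP4-6, 15% vs 25%, left out | about 6-8% | about 6-8% |
| TP1-3, 10% vs 30% | about 8-9% | – |

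The error falls in favour of whichever arm has more dropout, because its patients have less time in which to flare.

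**Step 3: the alternative.** Across 78 simulated null scenarios, including unequal dropout, a negative binomial model with log(days) offset gave 4.0-7.0%, and Poisson with robust variance and offset gave 4.0-6.8%.

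**The case against.** Much of the case on the other side stands.

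- The Poisson model is supplementary, and the ANOVA holds its level with equal observed time. At low flare rates and mild dispersion the Poisson error for TP4-6 is 6-7%, little different from the alternative.
- Unequal withdrawal is already examined. SAP 6.1 and 7.4.1 plan Kaplan-Meier curves of withdrawal by arm and tophus, and SAP 6.1 adds log-rank tests. These would reveal unequal dropout but not correct the flare tests for it.
- A reader might infer that nothing guides the handling of patients with no observed time, and so lead with the 14-32% figures. But the table conventions in SAP 11.2.5.2 base percentages on patients who have an observation or were assessed, and SAP 5.9 rules out default imputation. Neither names the flare models, but both lean towards leaving such patients out.
- A reader might infer that counting stops 30 days after the last dose, which would make observed time depend on drug stopping and could produce larger errors. The schedules have a separate flare row through TP6 Day 28, visits continue after drug withdrawal, and the model uses the ITT population. Counting to the end of TP6 is the natural reading.
- A reader might infer that entering follow-up as a covariate rather than an offset biases the treatment comparison. In the unequal-time scenarios the planned rate ratio stayed at 0.96-1.02 under equal true rates, so the effect is small.
- Calling the count the independent variable in SAP 7.2.5 and Protocol 13.4.2 is a slip; SAP 7.4.1 has it right.

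**Conclusion.** The point holds and is minor to moderate. As written, the Poisson test has a one-sided error of about 6-15% (TP4-6) or 7-21% (TP1-6) if counts are overdispersed to the assumed degree; the upper ends need the highest mean and the strongest variation. The ANOVA and the CMH incidence test are sound with equal observed time. Under 10% versus 30% dropout they move to about 7-11% for TP4-6 on the more likely handling of unobserved patients, and the TP1-3 ANOVA to about 8-9%. Flare rates, dispersion and dropout are all assumptions. The SAP expects more non-completers but does not say that they will differ by arm.

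A reader might infer that a confirmatory conclusion is at risk. The documents do not support that: the secondary endpoints have no hierarchy and the primary endpoint does not use flare data.

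**What to change.** In SAP 7.2.5 and 7.4.1 and Protocol 13.4.2:

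- Make the flare-frequency test for TP1-3, TP4-6 and TP1-6 a negative binomial regression, or Poisson with robust variance. Use flare count as the dependent variable, treatment and tophus stratum as factors, and log(days observed) as offset.
- Leave patients with no observed time in an interval out of that interval's model, and report their number by arm. The log offset is undefined at zero days in any case.
- Keep the ANOVA as descriptive.
- Reconcile the adverse-event wording (Protocol 11.2.1, 12.2.1.1 and 12.2.3.1; SAP 8.3) with the passages that follow patients to the end of TP6, so that one flare-counting window is stated, and define days observed to match.

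The cost is a small wording change to the SAP and protocol. No visits are added, because flares are already assessed at every visit. The downside is that p-values will be less favourable than from the unscaled Poisson model.
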